3. PARTICIPANT SELECTION

3.1 Eligibility Criteria

3.1.1 Participants must have histologically confirmed newly diagnosed glioblastoma or glioblastoma variant (ex. gliosarcoma), including documentation of unmutated isocitrate dehydrogenase (IDH) by immunohistochemistry or sequencing.

- 3.1.2 No prior immunotherapy allowed or prior alkylating agents or prior radiation to the brain.
- 3.1.3 Age >17 years since adult GBM is biologically different from pediatric GBM and there is no data for bavituximab in pediatric populations.
- 3.1.4 Karnofsky ≥60%, see Appendix A
- 3.1.5 Life expectancy of greater than 6 months.
- 3.1.6 Participants must have normal organ and marrow function as defined below:

_	leukocytes	≥3,000/mcL
_	absolute neutrophil count	$\geq 1.500/\text{mcL}$
_	platelets	≥100,000/mcL
_	total bilirubin	within normal institutional limits (unless patient has
	Gilbert's syndrome in which	total bilirubin should be $\leq 2xULN$
_	AST(SGOT)/ALT(SGPT)	$\leq 2.5 \times$ institutional upper limit of normal
_	creatinine	within normal institutional limits
		OR
-	creatinine clearance	\geq 60 mL/min/1.73 m ² for participants with creatinine
		levels above institutional normal(using Cockcroft Gault
		Formula)
-	negative serum pregnancy te	
-	INR/PT	- \leq 1.5 x institutional ULN unless subject is
		receiving anticoagulant therapy as long as PT or INR is within therapeutic range of intended use of
		anticoagulants
_	aPTT	\leq 1.5 x institutional ULN unless subject is receiving
		anticoagulant therapy as long as PTT is within
		therapeutic range of intended use of anticoagulants

- 3.1.7 < 4 mg dexamethasone daily (or equivalent if on another corticosteroid) at time of start of therapy. Patients on a steroid taper post-surgery and are anticipated to be on <4 mg at time of chemoradiation initiation will be eligible to consent but to initiate treatment on trial, the participant must be on <4 mg or equivalent of steroids otherwise participate will be deemed a screen fail and be replaced.
- 3.1.8 The effects of bavituximab on the developing human fetus are unknown. For this reason, women of child-bearing potential and men must agree to use adequate contraception (hormonal or barrier method of birth control; abstinence) prior to study entry and for the duration of study participation. Should a woman become pregnant or suspect she is pregnant while she or her partner is participating in this study, she should inform her treating physician immediately. Men treated or enrolled on this protocol must also agree to use adequate contraception prior to the study, for the duration of study participation, and 4 months after completion of bavituximab administration.

- 3.1.9 Able to undergo an MRI scan and receive gadolinium-based contrast.
- 3.1.10 1 cm3 of available tissue for N=5 patients for correlative tissue studies (Section 9.2.2). Patients can enroll regardless of their tissue availability being checked beforehand but at least 5 patients will need to have sufficient tissue by study accrual completion. Tissue availability will be checked after patients are successfully enrolled.
- 3.1.11 Ability to understand and the willingness to sign a written informed consent document.

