3.2 Exclusion Criteria

- 3.2.1 Participants who are receiving any other investigational agents.
- 3.2.2 History of allergic reactions attributed to compounds of similar chemical or biologic composition to bavituximab.
- 3.2.3 Participants receiving any medications or substances that are moderate and/or potent enzyme inducers or inhibitors which may have an effect on the metabolism of bavituximab. As part of the enrollment/informed consent procedures, the patient will be counseled on the risk of interactions with other agents, and what to do if new medications need to be prescribed or if the patient is considering a new over-the-counter medicine or herbal product (Appendix C for partial list).
- 3.2.4 Uncontrolled intercurrent illness including, but not limited to, ongoing or active infection, symptomatic congestive heart failure, unstable angina pectoris, cardiac arrhythmia, or psychiatric illness/social situations that would limit compliance with study requirements.
- 3.2.5 Pregnant women are excluded from this study because bavituximab is an immunotherapy agent with the potential for teratogenic or abortifacient effects. Because there is an unknown but potential risk for adverse events in nursing infants secondary to treatment of the mother with bavituximab breastfeeding should be discontinued if the mother is treated with bavituximab. These potential risks may also apply to other agents used in this study.

- 3.2.6 HIV-positive participants on combination antiretroviral therapy are ineligible because of the potential for pharmacokinetic interactions with bavituximab. In addition, these participants are at increased risk of lethal infections when treated with marrow-suppressive therapy.
- 3.2.7 Participants with other active malignancy in the past 3 years excluding in situ tumors.
- 3.2.8 Participants must meet the following windows from procedures (there is no window required for port placement since there is no anticipated impact on wound healing with bavituximab):

Major surgery (ex. craniotomy) within 3 weeks of initiation of treatment.Brain biopsy within 2 weeks

- 3.2.9 Participants with active bleeding disorder/coagulopathy.
- 3.2.10 Participants with active chronic or acute hepatitis C or B infection.

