As part of this protocol, patients will receive up to 2 cycles of adjuvant temozolomide at a dose of 150-200 mg/m2 days 1-5 of a 28-day cycle. Patients will be treated for up to 6 months of post-RT temozolomide (Stupp 2005). If patients experience grade 3 or higher toxicity attributable to the temozolomide that does not resolve to a grade 2 or less within 60 days of the last temozolomide dose, temozolomide should be discontinued. If the toxicity returns to a grade 2 or less within 30 days of the last dose, temozolomide can be dose reduced to 150mg/m2. The active period of this clinical trial will be approximately 18 weeks as long as there are no delays or missed doses that need to be made up.

As part of this protocol, temozolomide will be administered orally once per day for 5 consecutive days (days 1-5) of a 28-day cycle. The starting dose for the first cycle will be 150 mg/m²/day, with a single dose escalation to 200 mg/m²/day in subsequent cycles if no treatment-related adverse events > Grade 2 are noted. Patients can be increased to 200 mg/m2 at any time during the maintenance phase if deemed clinically appropriate by the treating physician.

The start of the cycle 2 will be scheduled 28 days \pm 7 days after the last day of radiotherapy. The start of the subsequent cycles (Cycles 3-4) will be scheduled in 28 days \pm 7 days) after the first daily dose of temozolomide of the preceding cycle.

The dose will be determined using the BSA per institutional standard.

Patients will be instructed to fast at least 2 hours before and 1 hour after temozolomide administration. Water is allowed during the fast period. Patients will be instructed to swallow the capsules whole, in rapid succession, without chewing them. Treatment can be given at night if patient prefers.

If vomiting occurs during the course of treatment, no re-dosing of the patient is allowed before the next scheduled dose.

If a patient misses the dose of temozolomide, it made be made up within 8 hours, otherwise the dose should be delayed until the next time it is due. Missed doses can be added on to the end of the 5 day dosing (i.e. taken on day 6) during the maintenance phase (i.e. 5/28 day cycles).

Antiemetic prophylaxis with a 5-HT3 antagonist is recommended and should be administered 30 to 60 minutes before temozolomide administration. Temozolomide should be stored at room temperature.

5.3.3 Other Modality(ies) or Procedures

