5.6 Duration of Follow Up

Participants will be followed every 3 months for 5 years from date of registration or until death, whichever occurs first. Participants removed from protocol therapy for unacceptable adverse event(s) will be followed until resolution or stabilization of the adverse event. Patients who do not continue to follow up in clinic will be reached by phone call to determine status. During this follow-up period, specific attention will be paid to any late effects of radiation which will be specifically captured on the case report forms.

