5.7 Criteria for Taking a Participant Off Study

Participants will be removed from study when any of the following criteria apply:

- Lost to follow-up
- Withdrawal of consent for data submission
- Death

The reason for taking a participant off study, and the date the participant was removed, must be documented in the case report form (CRF). The research team should also update the relevant Off Treatment/Off Study information in OnCore.

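### Section 3.1.8 sets a 4-month post-bavituximab contraception minimum for men but none for women of child-bearing potential, which leaves a narrow gap for a woman who leaves the study soon after her last dose

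*Combined protocol and SAP*

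**What the plan says.** Section 3.1.8 has two contraception sentences. The first covers women of child-bearing potential and men together and sets the period as "prior to study entry and for the duration of study participation". The second covers men only and sets it as before the study, "for the duration of study participation, and 4 months after completion of bavituximab administration". Between them is a notification duty that is also tied to participation: "Should a woman become pregnant or suspect she is pregnant while she or her partner is participating in this study", she is to tell her treating physician.

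The reasons given are that fetal effects of bavituximab are unknown (3.1.8) and that "bavituximab is an immunotherapy agent with the potential for teratogenic or abortifacient effects" (3.2.5). Section 3.2.5 adds: "These potential risks may also apply to other agents used in this study".

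The protocol does not define study participation, but three parts bear on it:

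- Section 5.5 lists reasons to stop protocol therapy. Section 5.7 has a separate list, opening "Participants will be removed from study when any of the following criteria apply", with three items: loss to follow-up, withdrawal of consent for data submission, and death.
- Section 5.6 states "Participants will be followed every 3 months for 5 years from date of registration or until death, whichever occurs first". The Section 10 calendar footnotes give survival follow-up of up to 3 years.
- The Section 10 footnotes blur this separation. In cycles 1 and 2 the column is for stopping treatment, but its footnote describes the patient as leaving the study. From cycle 3 on, meeting a Section 5.5 criterion is described as removal from the study.

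**The concern.** A fetus carried by a treated woman is exposed directly, yet only men have an explicit period counted from the last dose. The protocol gives no reason for the difference. It counts other safety periods from the last dose: 30 days for serious adverse events (7.3.1) and 30 days for toxicity (13.5.1).

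Because participation is undefined, what a woman has agreed to after her last dose depends on when she is taken to have left the study. If she leaves early, nothing in 3.1.8 extends beyond that point. The calendar schedules a pregnancy test only before the study, and the notification duty lapses with participation. The stake is an unprotected or unreported pregnancy soon after exposure. The efficacy result is not at stake.

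**Working it through.** There is no plan figure to reproduce. The check is a comparison of text followed by date arithmetic.

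**Step 1. Who is covered without a post-dose floor.** Take 18 weeks of dosing: 18 × 7 / 30.4 = about 4.1 months.

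- Participation through the 5-year follow-up (5.6), counted from about treatment start: 60 − 4.1 = about 56 months after the last dose.
- Participation through the 3-year follow-up (calendar): 36 − 4.1 = about 32 months.

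Both are far longer than 4 months, so a woman who remains in follow-up has no shortfall.

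**Step 2. Shortfall for a woman who leaves early.** The men's floor is 4 × 30.4 = 121.6 days, or 121.6 / 7 = 17.4 weeks. If her participation ends t weeks after her last dose, the shortfall is max(0, 17.4 − t). The worst case is t = 0, a complete exit at the last dose: 17.4 weeks.

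**Step 3. Allow for the monitoring in 13.5.1.** All participants are to be monitored for 90 days from completion of radiation, however long they received bavituximab. They are otherwise evaluable for toxicity until 30 days after the last dose. Count weeks from the start of radiation and assume six weeks of radiation (5.3.3) without delay. The 90-day period then ends at 6 + 90/7 = week 18.9. The 30-day period adds 30/7 = 4.3 weeks to the last dose. If participation lasts to the later of the two:

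| Last bavituximab dose | Participation ends | t (weeks) | Shortfall (weeks) |
|---|---|---|---|
| Week 1 | Week 18.9 | 17.9 | 0 |
| Week 6 | Week 18.9 | 12.9 | 4.5 |
| Week 10 | Week 18.9 | 8.9 | 8.5 |
| Week 18 | Week 22.3 | 4.3 | 13.1 |

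For the last row, 18 + 4.3 = week 22.3, which is later than week 18.9, so the 30-day period governs.

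**Step 4. Number of women.** The accrual target in 13.2 is 16 women among 36 participants. The documents give neither how many would be of child-bearing potential nor how many would leave within 4 months of the last dose. Section 13.1 expects very little loss to follow-up. No headcount follows from this.

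**The case against.** The strongest reply is that Sections 5.5 to 5.7 already settle the matter. Stopping therapy is not leaving the study. Only loss to follow-up, withdrawal of consent for data submission, or death ends participation, and follow-up runs for years. The calendar footnotes schedule visits and do not override 5.7. The rest of the protocol agrees: participants taken off therapy for adverse events are still followed (5.6), vital status at 12 months is sought even after drop-out (13.1), and the primary analysis is by intention to treat (13.5.2). Most of this stands, and it rules out the reading that women in general lose contraception cover when treatment ends. It does not reach a woman who meets a 5.7 criterion shortly after her last dose. It also does not prevent a site from following the footnote wording.

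A reader might infer from the men's 4-month clause that participation must end with treatment, since the clause would otherwise add little. That is suggestive but not proof, because the clause also protects men who leave early.

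A reader might also apply an assumed drop-out rate to the 16 targeted women to obtain a count. Both the rate and the share of child-bearing potential would be invented.

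Three further objections have some force:

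- Section 3.1.8 requires agreement, not verified use, and the study cannot monitor someone who has left. The value of a floor lies in what she was told and agreed to at entry.
- Section 7.3.2 already treats a congenital anomaly as a serious adverse event, including during post-treatment follow-up. That captures an outcome and does not prevent an exposure.
- The consent pages and the Investigator's Brochure were not available and may state a period for women. If so, 3.1.8 should agree with them.

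**Conclusion.** The point holds within narrow limits. Section 3.1.8 gives men a minimum counted from the last bavituximab dose and gives women of child-bearing potential none.

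The gap concerns a woman who is lost or withdraws consent within 4 months of her last dose, or whom a site treats as off study when therapy stops. Her shortfall against the men's rule is at most about 17.4 weeks, and that applies only to a complete exit at the last dose. It is smaller, and can be zero, if participation runs through the Section 13.5.1 monitoring. Those reduced figures assume undelayed six-week radiation and that she remains a participant until the monitoring ends.

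The number of women affected is probably very small and cannot be derived from the documents. The documents also do not show that 4 months is the right interval for women; it is only the men's figure used as a benchmark. The change is still worth making, because the possible harm is to a fetus and the remedy costs almost nothing.

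**What to change.** Amend 3.1.8 so that women of child-bearing potential agree to contraception throughout study participation and, in any case, for at least 4 months after completing bavituximab, or longer if the Investigator's Brochure requires it. Extend the pregnancy-notification duty over the same period. The 4 months is carried over from the men's rule because the documents give no separate interval for women.

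The floor should add to the participation duty and not replace it. Section 5.3.2 states "Patients will be treated for up to 6 months of post-RT temozolomide". Suppose monthly temozolomide starts at about week 10 and runs for six 28-day cycles. The last cycle then starts at week 10 + 5 × 4 = 30, with its fifth daily dose at about week 30.7. A bavituximab-only period for a woman who stopped at week 6 would end at 6 + 17.4 = week 23.4, while temozolomide could still be in use.

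The cost is a one-sentence amendment plus matching consent wording. OS12, the sample size and the analysis do not change.

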3.2 Exclusion Criteria

- 3.2.1 Participants who are receiving any other investigational agents.
- 3.2.2 History of allergic reactions attributed to compounds of similar chemical or biologic composition to bavituximab.
- 3.2.3 Participants receiving any medications or substances that are moderate and/or potent enzyme inducers or inhibitors which may have an effect on the metabolism of bavituximab. As part of the enrollment/informed consent procedures, the patient will be counseled on the risk of interactions with other agents, and what to do if new medications need to be prescribed or if the patient is considering a new over-the-counter medicine or herbal product (Appendix C for partial list).
- 3.2.4 Uncontrolled intercurrent illness including, but not limited to, ongoing or active infection, symptomatic congestive heart failure, unstable angina pectoris, cardiac arrhythmia, or psychiatric illness/social situations that would limit compliance with study requirements.
- 3.2.5 Pregnant women are excluded from this study because bavituximab is an immunotherapy agent with the potential for teratogenic or abortifacient effects. Because there is an unknown but potential risk for adverse events in nursing infants secondary to treatment of the mother with bavituximab breastfeeding should be discontinued if the mother is treated with bavituximab. These potential risks may also apply to other agents used in this study.

- 3.2.6 HIV-positive participants on combination antiretroviral therapy are ineligible because of the potential for pharmacokinetic interactions with bavituximab. In addition, these participants are at increased risk of lethal infections when treated with marrow-suppressive therapy.
- 3.2.7 Participants with other active malignancy in the past 3 years excluding in situ tumors.
- 3.2.8 Participants must meet the following windows from procedures (there is no window required for port placement since there is no anticipated impact on wound healing with bavituximab):

Major surgery (ex. craniotomy) within 3 weeks of initiation of treatment.Brain biopsy within 2 weeks

- 3.2.9 Participants with active bleeding disorder/coagulopathy.
- 3.2.10 Participants with active chronic or acute hepatitis C or B infection.

3.3 Inclusion of Women and Minorities

Both men and women of all races and ethnic groups are eligible for this trial.

4. **REGISTRATION PROCEDURES**

4.1 General Guidelines for DF/HCC Institutions

Institutions will register eligible participants in the Clinical Trials Management System (CTMS) OnCore. Registrations must occur prior to the initiation of protocol therapy. Any participant not registered to the protocol before protocol therapy begins will be considered ineligible and registration will be denied.

An investigator will confirm eligibility criteria and a member of the study team will complete the protocol-specific eligibility checklist.

Following registration, participants may begin protocol therapy. Issues that would cause treatment delays should be discussed with the Overall Principal Investigator (PI). If a participant does not receive protocol therapy following registration, the participant's registration on the study must be canceled. Registration cancellations must be made in OnCore as soon as possible.

4.2 Registration Process for DF/HCC Institutions

DF/HCC Standard Operating Procedure for Human Subject Research Titled *Subject Protocol Registration* (SOP #: REGIST-101) must be followed.

4.3 General Guidelines for Other Investigative Sites

Not applicable

4.4 Registration Process for Other Investigative Sites

Not applicable

5. TREATMENT PLAN

5.1 Treatment Regimen

Bavituximab will be administered weekly for 18 weeks starting the first week of chemoradiation. Patients may continue beyond 18 weeks at the discretion of the treating physician if the patient is deriving clinical benefit. Cycle 1 will encompass the 6 weeks of chemoradiation. Cycles 2 onward will be 4 weeks in length. Treatment will be administered on an outpatient basis. Reported adverse events and potential risks are described in Section 7. No investigational or commercial agents or therapies other than those described below may be administered with the intent to treat the participant's malignancy with the exception of NovoTTF.

Cycle 1: Chemoradiation

	Reg	gimen Desc	ription		
Agent	Premedications; Precautions	Dose	Route	Schedule	Cycle Length
Bavituximab	Optional: Premedicate with 250 mg hydrocortisone IV and 50 mg diphenhydramine IV administered ideally 30 minutes prior to infusion	3 mg/kg	First IV infusion must be administered over approximately 90 (±10) minutes. If the first IV infusion is tolerated, subsequent infusions may be administered over 60 (±10) minutes	Weekly starting with the 5 th day of radiation (window = after 4 th dose but before 6 th dose). Administra tion can be at any time of the day that fits the patient's schedule regardless of RT or temozolom	Cycle 1 6 weeks

				ide administrat ion.
Temozolomide	Zofran 4-8 mg or	75mg/m2	PO	Daily for
	other anti-emetic as			up to 42
	needed			days

Cycle 2: Post Radiation

	Reg	gimen Desc	ription			
Agent	Premedications; Precautions	Dose	Route	Schedule	Cycle Length	
Bavituximab	Optional: Premedicate with 250 mg hydrocortisone IV and 50 mg diphenhydramine IV administered ideally 30 minutes prior to infusion	3 mg/kg	IV infusion can be administered over approximately 60 (±10) minutes if the first IV infusion was tolerated. Otherwise continue at approximately 90 (±10) minutes.	Weekly	4 weeks	

Cycle 3 onward: With Monthly Temozolomide

	Reg	gimen Desc	ription			
Agent	Premedications; Precautions	Dose	Route	Schedule	Cycle Length	
Bavituximab	Optional:	3 mg/kg	IV infusion can	Weekly		
	Premedicate with 250		be administered			
	mg hydrocortisone		over			
	IV and 50 mg		approximately		4 weeks	
	diphenhydramine IV		60 (±10)		4 weeks	
	administered ideally		minutes if the			
	30 minutes prior to		first IV infusion			
	infusion		was tolerated.			
			Otherwise			
			continue at			

			approximately 90 (±10) minutes.	
Temozolomide	Zofran 4-8 mg or other anti-emetic as needed	150- 200mg/m2	РО	Daily for 5 consecutive days in cycles 3-4

5.2 **Pre-Treatment Criteria**

5.2.1 Cycle 1, Day 1

Prior to administration of the first dose of bavituximab on day 1 of cycle 1, participants must meet the following criteria:

- Signed informed consent
- Demographic information, medical history and concurrent medication list
- Physical examination including mini-mental status examination, vital signs, height, weight, and Karnofsky performance status
- Laboratory work meeting the eligibility criteria must be obtained.

